a: Includes possible, probable and definite. Source: Listing 16.X.X.X			

Clear Creek Bio, Inc.: Protocol CCB-CRISIS-01
Table 14.3.1.2
Summary of Treatment-Emergent Adverse Events by Treatment
Modified Intent-to-Treat Population

System Organ Class Preferred Term	SOC + Brequinar (N=xx)		SOC (N=xx)		Total (N=xx)	
	Subjects ^a n (%)	Events n	Subjects ^a n (%)	Events n	Subjects ^a n (%)	Events n
Any Adverse Event						
Overall	xx (xx.x)	xx	xx (xx.x)	xx	xx (xx.x)	xx
SOC 1						
Overall	xx (xx.x)	xx	xx (xx.x)	xx	xx (xx.x)	xx
Preferred Term 1	xx (xx.x)	xx	xx (xx.x)	xx	xx (xx.x)	xx
Preferred Term 2	xx (xx.x)	xx	xx (xx.x)	xx	xx (xx.x)	xx
Preferred Term 3	xx (xx.x)	xx	xx (xx.x)	xx	xx (xx.x)	xx
SOC 1						
Overall	xx (xx.x)	xx	xx (xx.x)	xx	xx (xx.x)	xx
Preferred Term 1	xx (xx.x)	xx	xx (xx.x)	xx	xx (xx.x)	xx
Preferred Term 2	xx (xx.x)	xx	xx (xx.x)	xx	xx (xx.x)	xx
Preferred Term 3	xx (xx.x)	xx	xx (xx.x)	xx	xx (xx.x)	xx
etc.						
a: Subjects experiencing one or more TEAEs are counted only once for each adverse event term. Source: Listing 16.X.X.X						

Programming note: Sort SOCs in descending frequency using total number of subjects in the SOC + Brequinar group, then sort preferred terms in descending frequency. Sort alphabetically to break ties.

Clear Creek Bio, Inc.: Protocol CCB-CRISIS-01

Table 14.3.1.7

Summary of Treatment-Emergent Adverse Events by Severity and Treatment
Modified Intent-to-Treat Population

System Organ Class Preferred Term	SOC + Brequinar (N=xx)						SOC (N=xx)					
	Subjects ^a n (%)	Grade 1 ^b n	Grade 2 ^b n	Grade 3 ^b n	Grade 4 ^b n	Grade 5 ^b n	Subjects ^a n (%)	Grade 1 ^b n	Grade 2 ^b n	Grade 3 ^b n	Grade 4 ^b n	Grade 5 ^b n
Overall												
Overall	xx (xx.x)	xx	xx	xx	xx	xx	xx (xx.x)	xx	xx	xx	xx	xx
SOC1												
Preferred Term 1	xx (xx.x)	xx	xx	xx	xx	xx	xx (xx.x)	xx	xx	xx	xx	xx
Preferred Term 2	xx (xx.x)	xx	xx	xx	xx	xx	xx (xx.x)	xx	xx	xx	xx	xx
Preferred Term 3	xx (xx.x)	xx	xx	xx	xx	xx	xx (xx.x)	xx	xx	xx	xx	xx
a: Subjects experiencing one or more TEAEs are counted only once for each adverse event term. b: Subjects experiencing one or more TEAEs are counted only once for each adverse event term and counted only by the maximum severity. Source: Listing 16.X.X.X												

Programming note: Sort SOC in descending frequency using total number of subjects in the SOC + Brequinar group, then sort preferred terms in descending frequency. Sort alphabetically to break ties.

Clear Creek Bio., Inc.: Protocol CCB-CRISIS-01

Table 14.3.2

Summary of Change from Baseline in Laboratory Parameters of Special Interest by Treatment and Visit
 Modified Intent-to-Treat Population

Parameter Visit	SOC + Brequinar (N=xx)		SOC (N=xx)	
	Visit	Change from Baseline	Visit	Change from Baseline
Parameter 1 (unit)				
Baseline				
n	xx		xx	
Mean (SE)	xx.x (xx.xx)		xx.x (xx.xx)	
Median	xx.x		xx.x	
Q1, Q3	xx.x, xx.x		xx.x, xx.x	
Min, Max	xx, xx		xx, xx	
Day 2				
n	xx	xx	xx	xx
Mean (SE)	xx.x (xx.xx)	xx.x (xx.xx)	xx.x (xx.xx)	xx.x (xx.xx)
Median	xx.x	xx.x	xx.x	xx.x
Q1, Q3	xx.x, xx.x	xx.x, xx.x	xx.x, xx.x	xx.x, xx.x
Min, Max	xx, xx	xx, xx	xx, xx	xx, xx
Day 3				
n	xx	xx	xx	xx
Mean (SE)	xx.x (xx.xx)	xx.x (xx.xx)	xx.x (xx.xx)	xx.x (xx.xx)
Median	xx.x	xx.x	xx.x	xx.x
Q1, Q3	xx.x, xx.x	xx.x, xx.x	xx.x, xx.x	xx.x, xx.x
Min, Max	xx, xx	xx, xx	xx, xx	xx, xx
etc.				
Parameter 2 (unit)				
Baseline				
Source: Listing 16.x.x.x				

Programming note: Include selected lab parameters: AST, ALT, ALP, Total Bilirubin, Creatinine, Hemoglobin, WBC, Absolute Neutrophils, Absolute

Clear Creek Bio, Inc.: Protocol CCB-CRISIS-01
Listing 16.2.1
Listing of End of Study Status by Treatment

Site-Subject	Date of Last Contact	Did the patient complete the study?	Primary Reason Did Not Complete	Comments
SOC + Brequinar				
xx-xxxx	9999-99-99	Yes		
xx-xxxx	9999-99-99	Yes		XXXXXXXXXXXXXXXX
SOC				
xx-xxxx	9999-99-99	No	XXXXXXXXXXXXXXXX	XXXXXXXXXXXXXXXX
xx-xxxx	9999-99-99	Yes		

Clear Creek Bio, Inc.: Protocol CCB-CRISIS-01

Listing 16.2.2

Listing of Inclusion/Exclusion Criteria and Randomization

Site-Subject	Does the subject meet all the Inclusion/Exclusion criteria?	Criterion Not Met	Comment / Explain Reason for Ineligibility	Date of Randomization	Time of Randomization	Treatment Assignment	ICU Level of Care at Randomization
xx-xxxx	Yes			9999-99-99	99:99	SOC	No
xx-xxxx	No	Exclusion 2 Inclusion 1	xxxxxxxxxx xxxxxxxxxx				Yes
xx-xxxx	Yes			9999-99-99	99:99	SOC + Brequinar	No
xx-xxxx	No	Inclusion 3	xxxxxxxxxx				No
xx-xxxx	Yes			9999-99-99	99:99	SOC + Brequinar	Yes
xx-xxxx	Yes			9999-99-99	99:99	SOC	No

Clear Creek Bio, Inc.: Protocol CCB-CRISIS-01

Listing 16.2.3

Listing of Informed Consent and Study Populations by Treatment

Site-Subject	Date of Informed Consent	Time of Informed Consent	Modified Intent-to-Treat Population ^a
SOC + Brequinar			
xx-xxxx	9999-99-99	99:99	Yes
xx-xxxx	9999-99-99	99:99	Yes
xx-xxxx	9999-99-99	99:99	Yes
SOC			
xx-xxxx	9999-99-99	99:99	xxx
xx-xxxx	9999-99-99	99:99	xxx
xx-xxxx	9999-99-99	99:99	xxx

a: Modified Intent-to-Treat (mITT) population includes all randomized subjects who had at least one post-randomization assessment, and who received at least one dose of study medication if randomized to SOC + Brequinar group.

Clear Creek Bio, Inc.: Protocol CCB-CRISIS-01

Listing 16.2.4.1

Listing of Subject Demographics by Treatment

Site-Subject	Date of Birth	Age (years)	Sex	Ethnicity	Race	Height (unit)	Weight (unit)	BSA (m2)
SOC + Brequinar								
xx-xxxx	9999-99-99	xx	Male	xxxxxxxxxxxxx	xxxxxxxxxxxxx	xxx (in)	xxx (lb)	x.x
xx-xxxx	9999-99-99	xx	Female	xxxxxxxxxxxxx	xxxxxxxxxxxxx	xxx (cm)	Not Done	
xx-xxxx	9999-99-99	xx	Male	xxxxxxxxxxxxx	Other: xxxxxxxxxxx	Not Done	xxx (kg)	
SOC								
xx-xxxx	9999-99-99	xx	xxxxx	xxxxxxxxxxxxx	xxxxxxxxxxxxx	xxxx	xxxx	x.x
xx-xxxx	9999-99-99	xx	xxxxx	xxxxxxxxxxxxx	xxxxxxxxxxxxx	xxxx	xxxx	x.x
xx-xxxx	9999-99-99	xx	xxxxx	xxxxxxxxxxxxx	Other: xxxxxxxxxxx	xxxx	xxxx	x.x

Clear Creek Bio, Inc.: Protocol CCB-CRISIS-01

Listing 16.2.4.2

Listing of Medical History by Treatment

Site-Subject	Diagnosis and/or Procedure	System Organ Class / Preferred Term	Onset Date	Resolution Date (Ongoing)
SOC + Brequinar				
xx-xxxx	COVID-19 xxxxxxxxxxxx	xxxxxxxxxxxx / xxxxxxxxxxxx xxxxxxxxxxxx / xxxxxxxxxxxx	9999-99-99 9999-99-99	Ongoing 9999-99-99
xx-xxxx	COVID-19			
SOC				
xx-xxxx	COVID-19 xxxxxxxxxxxx xxxxxxxxxxxx	xxxxxxxxxxxx / xxxxxxxxxxxx xxxxxxxxxxxx / xxxxxxxxxxxx xxxxxxxxxxxx / xxxxxxxxxxxx	9999-99-99 9999-99-99 9999-99-99	Ongoing 9999-99-99 9999-99-99
xx-xxxx	COVID-19	xxxxxxxxxxxx / xxxxxxxxxxxx	9999-99-99	Ongoing

Clear Creek Bio, Inc.: Protocol CCB-CRISIS-01

Listing 16.2.4.3

Listing of Prior and Concomitant Medications by Treatment

Site-Subject	M: Medication or Treatment ^a P: Pharmacological Subgroup C: Coded Term	Indication	Start Date	Stop Date (Ongoing)	Dose	Unit	Route	Prior/Con ^a
SOC + Brequinar								
xx-xxxx	M: xxxxxxxxxxxx P: xxxxxxxxxxxx C: xxxxxxxxxxxx	xxxxxxx	9999-99-99	9999-99-99	xxx	xxx	xxxxx	P
xx-xxxx	M: xxxxxxxxxxxx* P: xxxxxxxxxxxx C: xxxxxxxxxxxx	xxxxxxx	9999-99-99	Ongoing	xxx	xxx	Other: xxxxx	P, C
	M: xxxxxxxxxxxx P: xxxxxxxxxxxx C: xxxxxxxxxxxx	xxxxxxx	9999-99-99	9999-99-99	xxx	xxx	xxxxx	C
SOC								
xx-xxxx	None							
xx-xxxx	M: xxxxxxxxxxxx* P: xxxxxxxxxxxx C: xxxxxxxxxxxx	xxxxxxx	9999-99-99	Ongoing	xxx	Other: xxx	xxxxx	C
a: P=Prior medication, C=Concomitant medication. A prior medication is any medication that started prior to date of randomization. A concomitant medication is any medication that either has a start date on or after date of randomization, or is ongoing on the date of randomization.								

Programming Note: Pharmacological Subgroup comes from ATC3. If ATC3 is not available, use ATC2.

Clear Creek Bio, Inc.: Protocol CCB-CRISIS-01

Listing 16.2.4.4

Listing of Prior and Concomitant Procedures by Treatment

Site-Subject	P: Procedure S: System Organ Class T: Preferred Term	Indication	Start Date	Stop Date (Ongoing)	Dose	Unit	Route	Prior/Con ^a
SOC + Brequinar								
xx-xxxx	P: xxxxxxxxxxxx S: xxxxxxxxxxxx T: xxxxxxxxxxxx	xxxxxxx	9999-99-99	9999-99-99	xxx	xxx	xxxxx	P
xx-xxxx	P: xxxxxxxxxxxx S: xxxxxxxxxxxx T: xxxxxxxxxxxx	xxxxxxx	9999-99-99	Ongoing	xxx	xxx	Other: xxxxx	P, C
	P: xxxxxxxxxxxx S: xxxxxxxxxxxx T: xxxxxxxxxxxx	xxxxxxx	9999-99-99	9999-99-99	xxx	xxx	xxxxx	C
SOC								
xx-xxxx	None							
xx-xxxx	P: xxxxxxxxxxxx S: xxxxxxxxxxxx T: xxxxxxxxxxxx	xxxxxxx	9999-99-99	Ongoing	xxx	Other: xxx	xxxxx	C
a: P=Prior procedure, C=Concomitant procedure. A prior procedure is any procedure that started prior to date of randomization. A concomitant procedure is any procedure that either has a start date on or after date of randomization, or is ongoing on the date of randomization.								

Clear Creek Bio, Inc.: Protocol CCB-CRISIS-01

Listing 16.2.5.1

Listing of Dosing Information (SOC + Brequinar Only)

Site-Subject	Day 1		Day 2		Day 3		Day 4		Day 5	
	Date of Dosing	Time of Dosing	Date of Dosing	Time of Dosing	Date of Dosing	Time of Dosing	Date of Dosing	Time of Dosing	Date of Dosing	Time of Dosing
xx-xxxx	9999-99-99	99:99	Not Done		9999-99-99	99:99	9999-99-99	99:99	9999-99-99	99:99
xx-xxxx	9999-99-99	99:99	9999-99-99	99:99	9999-99-99	99:99	9999-99-99	99:99	9999-99-99	99:99
xx-xxxx	9999-99-99	99:99	9999-99-99	99:99	9999-99-99	99:99	9999-99-99	99:99	Not Done	
xx-xxxx	Not Done		9999-99-99	99:99	9999-99-99	99:99	9999-99-99	99:99	9999-99-99	99:99

Clear Creek Bio, Inc.: Protocol CCB-CRISIS-01

Listing 16.2.5.2

Listing of PK/DHO Results by Treatment

Site-Subject	Visit	Not Done	Date Collected	Time Collected	PK Result (mcg/mL) ^a	DHO Result (ng/mL) ^a
SOC + Brequinar						
xx-xxxx	Day 1		9999-99-99	99:99	xxx	xxxx
	Day 3		9999-99-99	99:99	xxx	xxxx
	Day 5	Not Done				
	Day 7		9999-99-99	99:99	xxx	xxxx
	Day 15		9999-99-99	99:99	xxx	xxxx
SOC						
xx-xxxx	Day 1		9999-99-99	99:99	BLOQ (<5)	xxxx
	Day 3		9999-99-99	99:99	xxx	xxxx
	Day 5		9999-99-99	99:99	xxx	xxxx
	Day 7		9999-99-99	99:99	xxx	BLOQ (<5)
	Day 15		9999-99-99	99:99	xxx	xxxx
a: BLOQ = Below Limit of Quantification (limit of quantification in parentheses)						

Clear Creek Bio, Inc.: Protocol CCB-CRISIS-01

Listing 16.2.6.1

Listing of NEWS2 Assessments by Treatment

Site-Subject	Visit	Date and Time Collected	SBP ^a (mmHg)	DBP ^a (mmHg)	Pulse (Beats/Min.)	Respiration (Breath/Min.)	SpO ₂ / SaO ₂ (%)	Temp. (Celsius)	Supplemental Oxygen?	Hypercapnic respiratory failure?	Alert?	NEWS 2 Score
SOC + Brequinar												
xx-xxxx	Day 1	9999-99-99T99:99	xxx	xxx	ND	xxx	xxx	xx.x	Yes	Yes	Yes	xx
	Day 3	9999-99-99T99:99	xxx	xxx	xxx	xxx	xxx	xx.x	Yes	No	No	xx
	Day 5	9999-99-99T99:99	xxx	xxx	xxx	xxx	ND	xx.x	No	Yes	No	xx
	Day 7	Not Done										
	Day 15	9999-99-99T99:99	xxx	xxx	xxx	xxx	xxx	xx.x	No	Unknown	Yes	xx
SOC												
xx-xxxx	Day 1	9999-99-99T99:99	xxx	xxx	xxx	ND	xxx	xx.x	xxx	xxx	xxx	xx
	Day 3	9999-99-99T99:99	xxx	xxx	xxx	xxx	xxx	ND	xxx	xxx	xxx	xx
	Unscheduled											
	Day 5	9999-99-99T99:99	xxx	xxx	xxx	xxx	xxx	xx.x	xxx	xxx	xxx	xx
	Day 7	9999-99-99T99:99	ND	ND	xxx	xxx	xxx	xx.x	xxx	xxx	xxx	xx
	Day 15	9999-99-99T99:99	xxx	xxx	xxx			xx.x	xxx	xxx	xxx	xx
Note: ND=Not Done a: SBP=Systolic Blood Pressure, DBP=Diastolic Blood Pressure.												

Clear Creek Bio, Inc.: Protocol CCB-CRISIS-01

Listing 16.2.6.2

Listing of Inflammatory Markers by Treatment

Parameter	Visit	Not Done	Laboratory	Date and Time Collected	Result	Abnormal?	Reference Range	
SOC + Brequinar								
Site-Subject= xx-xxxx								
Parameter 1 (unit)	Day 1	Not Done	Local	9999-99-99T99:99	xx.x	High		
	Day 3		Local	9999-99-99T99:99	xx.x	High		
	Day 5		Central	9999-99-99T99:99	xx.x			
	Day 7							
	Day 15		Local	9999-99-99T99:99	xx.x			
Parameter 2 (unit)	Day 1	Not Done	Local	9999-99-99T99:99	xx.x	Abnormal		
	Day 3		Local	9999-99-99T99:99	xx.x			
	Unscheduled		Local	9999-99-99T99:99	xx.x			
	Day 5		Local	9999-99-99T99:99	xx.x			
	Day 7							
	Day 15		Local	9999-99-99T99:99	xx.x			
SOC								
Site-Subject= xx-xxxx								
Parameter 1 (unit)	Day 1		Central	9999-99-99T99:99	xx.x			
	Day 3		Central	9999-99-99T99:99	xx.x			
	Day 5		Central	9999-99-99T99:99	xx.x			
	Day 7		Central	9999-99-99T99:99	xx.x			
	Day 15		Central	9999-99-99T99:99	xx.x			

Programming note: Include all data collected in local and central labs, including the tests done in both labs or done multiple times.

Clear Creek Bio, Inc.: Protocol CCB-CRISIS-01
Listing 16.2.6.3
Listing of SARS-CoV-2 Viral Load and Viral Cultureunit by Treatment

Site-Subject	Visit	Not Done	Date Collected	Time Collected	Viral Load (copies/mL)	Viral Culture (unit)
SOC + Brequinar						
xx-xxxx	Day 1		9999-99-99	99:99		
	Day 3		9999-99-99	99:99		
	Day 5	Not Done				
	Day 7		9999-99-99	99:99		
	Day 15		9999-99-99	99:99		
SOC						
xx-xxxx	Day 1		9999-99-99	99:99		
	Day 3		9999-99-99	99:99		
	Day 5		9999-99-99	99:99		
	Day 7		9999-99-99	99:99		
	Day 15		9999-99-99	99:99		

Clear Creek Bio, Inc.: Protocol CCB-CRISIS-01
Listing 16.2.6.4
Listing of Hospitalization Log by Treatment

Site-Subject	Event Type	Event Date
SOC + Brequinar		
xx-xxxx	xxxxxxxxxxxxx	9999-99-99
xx-xxxx	xxxxxxxxxxxxx	9999-99-99
	Other: xxxxxxxxxxxxx	9999-99-99
	xxxxxxxxxxxxx	
SOC		
xx-xxxx	None	
xx-xxxx	Other: xxxxxxxxxxxxx	9999-99-99
	xxxxxxxxxxxxx	

Clear Creek Bio, Inc.: Protocol CCB-CRISIS-01

Listing 16.2.6.5

Listing of Survival Status by Treatment

Site-Subject	Visit	Date of Contact	Survival Status	Date of Death	Not Done, Comment
SOC + Brequinar					
xx-xxxx	Day 1 – Day 15		Alive		
	Day 29 Contact	9999-99-99	Alive		
xx-xxxx	Day 1 – Day 15		Patient Died	9999-99-99	
xx-xxxx	Day 1 – Day 15		Alive		
	Day 29 Contact				Not Done: xxxxxxxxxxxxxxxxx
SOC					
xx-xxxx	Day 1 – Day 15		Alive		
	Day 29 Contact	9999-99-99	Patient Died	9999-99-99	
xx-xxxx	Day 1 – Day 15		Alive		
	Day 29 Contact	9999-99-99	Alive		

Clear Creek Bio, Inc.: Protocol CCB-CRISIS-01

Listing 16.2.7.1

Listing of Adverse Events by Treatment

Site-Subject	Adverse Event Term/ System Organ Class/ Preferred Term	Onset Date and Time/ Resolution Date and Time	Continuing?	Outcome ^a	Severity	Causality	Action Taken with Study Treatment	Action Taken	Serious?
SOC + Brequinar									
xx-xxxx	xxxxxxx/ xxxxxxx / xxxxxxx*	9999-99-99T99:99/ 9999-99-99T99:99	Continuous	RG	Grade 2	Definite	Drug Interrupted	None	No
xx-xxxx	xxxxxxx/ xxxxxxx / xxxxxxx	9999-99-99T99:99/ 9999-99-99T99:99	Intermittent	RD	Grade 4	Probable	Drug Withdrawn	Treatment Prescribed	No
	xxxxxxx/ xxxxxxx / xxxxxxx	9999-99-99T99:99/ 9999-99-99T99:99	Continuous	RS	Grade 1	Possible	Unknown	Discontinued Study	No
SOC									
xx-xxxx	xxxxxxx/ xxxxxxx / xxxxxxx	9999-99-99T99:99/ 9999-99-99T99:99	Intermittent	NR	Grade 5	Unlikely	Not Applicable	Treatment Prescribed, Discontinued Study	Yes
	xxxxxxx/ xxxxxxx / xxxxxxx	9999-99-99T99:99/ 9999-99-99T99:99	Continuous	UN	Grade 3	Unrelated	Dose Not Changed	None	No

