2. STATISTICAL METHODOLOGY

2.1 General Principles

In general, continuous parameters will be summarized by number of non-missing observations (N), mean, standard error (SE), median, quartiles, minimum, and maximum. Categorical parameters will be summarized by count and percentage of the non-missing observations, and

Confidential Document

	CCB-CRISIS-01 Statistical Analysis Plan	Revision No. 1.0
	Document Date: 17-Dec-2020	Page 8 of 17

95% confidence interval (CI), when appropriate. All statistical analyses will be performed using SAS® Version 9.4. Adverse events (AEs), procedures and medical history will be coded using Medical Dictionary for Regulatory Activities (MedDRA) Version 23.0. Prior and concomitant medications will be coded using World Health Organization Drug Dictionary (WHODrug) Enhanced March 2020. Common Terminology Criteria for Adverse Events (CTCAE) Version 4.03 will be utilized for adverse event and laboratory reporting.

All study data collected will be presented in listings.

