2.6 Safety Analyses

Adverse Events

An overall summary of treatment-emergent adverse events (TEAEs) will be presented by treatment and total, including the total number of events, frequency counts and percentages for:

- Any TEAE
- Treatment-related TEAEs
- CTCAE Grade 3 or above TEAEs
- TEAEs leading to drug withdrawn
- TEAEs leading to study discontinuation
- Serious TEAEs
- Fatal TEAEs
- TEAEs of interest

The incidence of TEAEs by treatment and total will be tabulated by MedDRA system organ class and preferred term for:

- All TEAEs
- Treatment-related TEAEs
- TEAEs by severity
- TEAEs leading to study discontinuation
- Serious TEAEs
- TEAEs of interest

AEs will be considered treatment-emergent if the onset date is on or after the day of randomization. “Drug related” will include ‘Definite’, ‘Probable’ and ‘Possible’ relationship to drug as determined by the Investigator.

Safety Laboratory Assessments

Safety laboratory tests (Chemistry and Hematology) will be performed throughout the study. Laboratory parameters of interest (AST, ALT, ALP, Total Bilirubin, Creatinine, Hemoglobin, WBC, Absolute Neutrophils, Absolute Lymphocytes and Platelets) will be summarized for changes from baseline.

Confidential Document

	CCB-CRISIS-01 Statistical Analysis Plan	Revision No. 1.0
	Document Date: 17-Dec-2020	Page 11 of 17

NCI CTCAE grades will be derived for the lab parameters included in [Appendix 1](#) and presented in data listings. Separate listings of Grade 3 or 4 values will also be provided.

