3. DATA HANDLING

3.1 Baseline and Study Visits

Study Day 1 will be the day of randomization.

The summary of hospitalization status will be based on the Study Day (derived relative to the day of randomization).

For the summary of inflammatory markers, Baseline will be the last assessment prior to dosing (SOC plus brequinar group) or last assessment on or prior to Study Day 1 (SOC group). Post-baseline timepoints will be based on the Study Day (derived relative to the day of randomization), where Day 15 includes a 4-day window (Study Day 11-19). If there are multiple results on the same day, the earliest result will be used.

For all other summaries, post-baseline timepoints will use the visit as recorded on the case report form, and Baseline will be the last non-missing value prior to randomization, including unscheduled assessments. Otherwise, unscheduled data will not be used in the analyses, but will be presented in the listings.

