APPENDIX 1 CTCAE V4.03 GRADING FOR LABORATORY VALUES

Lab Test	Lab Unit	Grade 1	Grade 2	Grade 3	Grade 4
Albumin	G/DL	3 to <LLN	2 to <3	<2	Clinical Review Needed: Life-threatening consequences; urgent intervention indicated
Alkaline Phosphatase	U/L	>ULN to 2.5xULN	>2.5xULN to 5xULN	>5xULN to 20xULN	>20xULN
Alanine Amino Transferase	U/L	>ULN to 3xULN	>3xULN to 5xULN	>5xULN to 20xULN	>20xULN
Aspartate Amino Transferase	U/L	>ULN to 2.5xULN	>2.5xULN to 5xULN	>5xULN to 20xULN	>20xULN
Bilirubin Total	MG/DL	>ULN to 1.5xULN	>1.5xULN to 3xULN	>3xULN to 10xULN	>10xULN
Calcium	MG/DL	>ULN to 11.5	>11.5 to 12.5	>12.5 to 13.5	>13.5
Calcium	MG/DL	8 to <LLN	7 to <8	6 to <7	<6
Creatinine	MG/DL	>ULN to 1.5xULN	>1.5xULN to 3xULN	>3xULN to 6xULN	>6xULN
Glucose	MG/DL	>ULN to 160	>160 to 250	>250 to 500	>500
Glucose	MG/DL	55 to <LLN	40 to <55	30 to <40	<30
Potassium	MMOL/L	>ULN to 5.5	>5.5 to 6	>6 to 7	>7

Confidential Document

Lab Test	Lab Unit	Grade 1	Grade 2	Grade 3	Grade 4
Potassium	MMOL/L	Clinical Review Needed: Check Grade 2 and reassign if not symptomatic and no intervention indicated	3 to <LLN	2.5 to <3	<2.5
Sodium	MMOL/L	>ULN to 150	>150 to 155	>155 to 160	>160
Sodium	MMOL/L	130 to <LLN	-	120 to <130	<120
Lymphocytes, Absolute	10 ³ /UL	-	>4 to 20	>20	-
Lymphocytes, Absolute	10 ³ /UL	0.8 to <LLN	0.5 to <0.8	0.2 to <0.5	<0.2
Neutrophils, Absolute	10 ³ /UL	-	-	<1	Clinical Review Needed: Life-threatening consequences; urgent intervention indicated
Neutrophils, Absolute	10 ³ /UL	1.5 to <LLN	1 to <1.5	0.5 to <1	<0.5
Hemoglobin	G/DL	>0 to 2	>2 to 4	>4	
Hemoglobin	G/DL	>ULN to ULN+2	>ULN+2 to ULN+4	>ULN+4	
Hemoglobin	G/DL	10 to <LLN	8 to <10	<8	Clinical Review Needed: Life-threatening consequences; urgent intervention indicated
Platelet Count	10 ³ /UL	75 to <LLN	50 to <75	25 to <50	<25

Confidential Document

	CCB-CRISIS-01 Statistical Analysis Plan	Revision No. 1.0
	Document Date: 17-Dec-2020	Page 17 of 17

Lab Test	Lab Unit	Grade 1	Grade 2	Grade 3	Grade 4
White Blood Cell	10 ³ /UL	-	-	>100	Clinical Review Needed: Clinical manifestations of leucostasis; urgent intervention indicated
White Blood Cell	10 ³ /UL	3 to <LLN	2 to <3	1 to <2	<1

Note: For these laboratory tests, Grade 0 is assigned if result does not meet above ranges.

Confidential Document

**CLEAR CREEK BIO. INC.
PROPOSED TABLES and LISTINGS
PROTOCOL CCB-CRISIS-01**

**Version 1.0
17-Dec-2020**

[figure not shown]

**CLEAR CREEK BIO. INC.
PROPOSED TABLES and LISTINGS
PROTOCOL CCB-CRISIS-01**

**Version 1.0

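### Appendix 1 grades creatinine against the ULN alone, so a doubling that stays at or below the ULN is Grade 0, while a stable pre-existing value above 3 x ULN is listed as Grade 3 or 4 at every visit

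*SAP*

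**What the plan says.** Section 2.1 of the SAP names the grading standard: CTCAE "Version 4.03 will be utilized for adverse event and laboratory reporting". Section 2.6 states that "NCI CTCAE grades will be derived for the lab parameters included in" Appendix 1 and shown in data listings, and adds that "Separate listings of Grade 3 or 4 values will also be provided".

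Appendix 1 has one creatinine row, in mg/dL:

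- Grade 1: ">ULN to 1.5xULN"
- Grade 2: ">1.5xULN to 3xULN"
- Grade 3: ">3xULN to 6xULN"
- Grade 4: anything above 6 x ULN

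The note under the table closes the scale: "Grade 0 is assigned if result does not meet above ranges".

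Creatinine is one of the ten laboratory parameters of interest in Section 2.6, and Table 14.3.2 summarizes its change from baseline. Section 3.1 supplies the baseline that applies to it: "Baseline will be the last non-missing value prior to randomization, including unscheduled assessments". The grading row does not use that baseline.

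**The concern.** A ULN-only rule compares a subject with the laboratory's reference range and never with that subject's own starting value. For creatinine this can mislead in two directions. A subject who starts low can have a large relative rise without leaving Grade 0. A subject who starts well above the ULN and does not change is graded as severe at each visit, and the grade itself does not show that the value predates treatment.

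Safety and tolerability are the primary objective (Section 1.3.1), and the planned arms are about 16 and 8 subjects (Section 1.2.1). At that size laboratory safety will be read subject by subject, and the Grade 3 or 4 listings are the laboratory outputs that single subjects out. What is at stake is whether they single out the right ones.

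**Working it through.** **Inputs.** The cut-points of 1, 1.5, 3 and 6 x ULN and the Grade 0 rule come from Appendix 1. The SAP gives no creatinine ULN or lower limit of normal (LLN), so the ULN is an assumption, taken as 1.0 to 1.5 mg/dL. There is no sample size, power or error-rate figure to reproduce.

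**Rises that stay ungraded.** A value at or below the ULN is Grade 0. An m-fold rise from baseline B is therefore Grade 0 when m x B <= ULN, that is when B <= ULN/m.

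| Assumed ULN (mg/dL) | Doubling is Grade 0 if B <= ULN/2 | Tripling is Grade 0 if B <= ULN/3 | Stable value is Grade 3 if above 3 x ULN, up to 6 x ULN |
|---|---|---|---|
| 1.0 | 0.50 | 0.33 | 3.0 to 6.0 |
| 1.2 | 0.60 | 0.40 | 3.6 to 7.2 |
| 1.3 | 0.65 | 0.43 | 3.9 to 7.8 |
| 1.5 | 0.75 | 0.50 | 4.5 to 9.0 |

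**Fold rise needed for each grade, ULN 1.2.** The largest rise still at Grade 0 is ULN/B. Grade 2 needs more than 1.5 x ULN/B, and Grade 3 more than 3 x ULN/B.

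| Baseline (mg/dL) | Grade 0 up to | Grade 2 above | Grade 3 above |
|---|---|---|---|
| 0.4 | 3.0-fold | 4.5-fold | 9.0-fold |
| 0.5 | 2.4-fold | 3.6-fold | 7.2-fold |
| 0.6 | 2.0-fold | 3.0-fold | 6.0-fold |
| 0.8 | 1.5-fold | 2.25-fold | 4.5-fold |

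For a baseline of 0.5, the Grade 0 ceiling moves from 1.0/0.5 = 2.0-fold to 1.3/0.5 = 2.6-fold as the assumed ULN goes from 1.0 to 1.3.

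**Stable elevated values, ULN 1.2.**

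- 1.8/1.2 = 1.5, Grade 1
- 2.0/1.2 = 1.67 and 3.0/1.2 = 2.5, Grade 2
- 4.0/1.2 = 3.33, Grade 3
- 8.0/1.2 = 6.67, Grade 4

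Only stable values above 3 x ULN reach the Grade 3 or 4 listing at every visit.

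**Whether another output fills the gap.** Table 14.3.2 reports absolute change by arm. A maximum change of 0.7 mg/dL could be 0.5 to 1.2 (2.4-fold) or 4.0 to 4.7 (about 1.2-fold), and the table cannot tell these apart. Listing 16.2.8.1.1 prints each value with a reference range, an abnormal flag and the grade, but has no baseline or change column. A doubling that stays within range would appear there with no flag and Grade 0.

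**The case against.** The strongest reply is that nothing is lost and nothing is estimated from these grades. Section 2.6 puts them in listings only. No table shell counts them, and Table 14.3.1.7 tabulates adverse-event severity, not laboratory grade. Listing 16.2.8.1.1 shows each subject's values in visit order (Days 1 to 7 and 15), so in about 24 subjects a rise from 0.5 to 1.2 can be found by eye. Table 14.3.2 gives the minimum and maximum change, so the same rise would make the arm's maximum at least 0.7 mg/dL. The Grade 3 or 4 listing is not restricted to post-baseline values, so a graded Day 1 result may stand beside the later ones and show that nothing changed. One such subject adds at most eight scheduled rows. All of this stands. It limits the point to flagging and makes it minor.

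It is also fair that ALT, AST, ALP and bilirubin are graded on the ULN alone, and that no internal contradiction is shown.

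A reader might infer three stronger claims that the SAP does not support:

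- **Unchanged chronic impairment is always Grade 3.** This holds only above 3 and up to 6 x ULN. Milder stable elevation is Grade 1 or 2, and higher values are Grade 4.
- **A tripling within the normal range is Grade 0.** A tripling at Grade 0 needs a baseline at or below ULN/3. It lies wholly within the normal range only if ULN/LLN is at least 3, and no LLN is given.
- **The row departs from the published CTCAE v4.03 criterion.** That cannot be checked from the SAP, and the point does not rest on it.

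**Conclusion.** The point holds as a limitation of a rule the SAP states explicitly. A creatinine doubling that stays at or below the ULN is Grade 0 and cannot reach the Grade 3 or 4 listing. A stable pre-existing value above 3 x ULN is listed as Grade 3 or 4 at every visit. The mechanism follows from Appendix 1 alone; the mg/dL figures depend on the assumed ULN of 1.0 to 1.5.

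How often either case would occur cannot be estimated. The SAP gives no baseline creatinine distribution, and any renal eligibility limit would be in the protocol, which was not available for this check. Such a limit could make the stable high value rare, but would not touch the low-baseline case.

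The consequence is one of display. No estimate, incidence or comparison changes, and raw values remain visible. What is missing is an output that flags a relative rise in an individual subject. Severity is minor. The change is worth making because safety is the primary objective and the baseline it needs is already defined.

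**What to change.** In Appendix 1, add a baseline-relative grade for post-baseline creatinine, using the Section 3.1 baseline and multipliers already in the row:

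- above 1.5x and up to 3x baseline: Grade 2
- above 3x baseline: at least Grade 3

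Report the higher of this and the ULN-based grade. Use the ULN-based grade alone when baseline is missing, since Section 3.3 plans no imputation. Show which criterion, ULN or baseline, produced the grade. In the Grade 3 or 4 chemistry listing, add the baseline value and mark results whose grade is no higher than at baseline.

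Effect with ULN 1.2: a rise from 0.5 to 1.2 (2.4-fold) moves from Grade 0 to Grade 2. It is then graded in Listing 16.2.8.1.1 but still does not enter the Grade 3 or 4 listing; only rises above 3-fold do so on the new criterion. A stable 4.0 stays Grade 3 and is marked as no worse than at baseline.

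The cost is one row of Appendix 1, a few lines in the grading program and small additions to the listings, with no new data. The downside is that some small absolute rises from a low baseline will carry a high grade. For example, 0.4 to 1.21 mg/dL is 1.21/0.4 = 3.03-fold and becomes Grade 3, although it is barely above an ULN of 1.2. Showing the criterion lets a reader recognize such cases.

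### Two hematology rows in SAP Appendix 1 fail as written: one makes every hemoglobin above 4 g/dL Grade 3, the other gives neutrophil counts below 0.5 two grades

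*SAP*

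**What the plan says.** Section 2.6 of the SAP, under safety laboratory assessments, says that "NCI CTCAE grades will be derived for the lab parameters included in" Appendix 1, that they appear in data listings, and that Grade 3 or 4 values get separate listings. For hematology the separate listing is 16.2.8.2.2. The same section names hemoglobin and absolute neutrophils among the laboratory parameters of interest.

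Appendix 1 has columns for test, unit and Grades 1 to 4. It gives hemoglobin three rows:

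- first row: "Hemoglobin G/DL >0 to 2 >2 to 4 >4"
- second row: "Hemoglobin G/DL >ULN to ULN+2 >ULN+2 to ULN+4 >ULN+4"
- third row: "Hemoglobin G/DL 10 to <LLN 8 to <10 <8", with Grade 4 left to clinical review

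It gives neutrophils two rows, in 10³/µL:

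- first row: "Neutrophils, Absolute 10 ³ /UL - - <1", with Grade 4 again left to clinical review
- second row: "1.5 to <LLN 1 to <1.5 0.5 to <1 <0.5" for Grades 1 to 4

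The note under the table assigns Grade 0 to a result that falls in none of the listed ranges. Neither the appendix nor the body of the SAP says what to do when a result falls in two rows at once.

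**The concern.** The first hemoglobin row has limits of 2 and 4 with no statement of what they are measured from. A programmer who applies it to the reported value grades normal hemoglobin as severe toxicity. Its cut-points recur in the second row as ULN+2 and ULN+4, which suggests a scale of increases whose reference was left out, but the SAP does not say so.

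The two neutrophil rows both grade low counts and disagree below 0.5. Other tests with two rows (calcium, glucose, potassium, sodium, lymphocytes, white cells) have one for high and one for low values, so their rows do not collide.

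At stake is the usefulness of the graded hematology listings for two parameters the plan itself singles out, in a trial whose primary objective (Section 1.3.1) is safety and tolerability. If the rows are followed, the Grade 3 or 4 listing does not discriminate. If they are quietly repaired in programming, the grading rests on an undocumented choice in an open-label trial.

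**Working it through.** The plan states no figure to reproduce here. The check applies each row literally to a set of values.

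**Inputs.** The row limits come from Appendix 1. The SAP gives no normal ranges, so two were assumed for hemoglobin: 12 to 16 and 13.5 to 17.5 g/dL. The collisions themselves do not depend on these ranges.

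**Hemoglobin (g/dL).** A dash means that no range in that row is met.

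| Value | First row | Second row (high) | Third row (low) |
|---|---|---|---|
| 1 | Grade 1 | – | Grade 3 |
| 3 | Grade 2 | – | Grade 3 |
| 7.5 | Grade 3 | – | Grade 3 |
| 9 | Grade 3 | – | Grade 2 |
| 11 | Grade 3 | – | Grade 1 |
| 14 | Grade 3 | – | – |

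These entries are the same under both assumed ranges. Three things follow.

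1. The first row covers every value above 0, so the Grade 0 note can never apply to a positive hemoglobin.
2. The first row assigns Grade 3 to everything above 4 and the third row to everything below 8. Together they leave no value without a Grade 3 from at least one row.
3. The conflict runs both ways. At 9, 11 and 14 the first row is the more severe; at 1 and 3 it is the less severe.

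**Effect of removing the first row.** Take a grid from 6.0 to 20.0 in steps of 0.1, which has 141 points. With all three rows, 141/141 = 100% carry a Grade 3. Without the first row, only values below 8 do (6.0 to 7.9, 20 points), because ULN+4 is 20 or 21.5 under the assumed ranges and no grid point exceeds it. The share is 20/141 = 14.2%. This is a share of a grid of values, not a forecast for patients.

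**Neutrophils (10³/µL).**

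| Value | First row | Second row |
|---|---|---|
| 0.3 | Grade 3 | Grade 4 |
| 0.49 | Grade 3 | Grade 4 |
| 0.5 | Grade 3 | Grade 3 |
| 0.7 | Grade 3 | Grade 3 |
| 1.2 | – | Grade 2 |

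The rows disagree on every count below 0.5, agree from 0.5 to below 1, and do not overlap from 1 upward. Every count below 1 is Grade 3 or 4 under either row, so no neutrophil result enters or leaves the Grade 3 or 4 listing.

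**The case against.** The case for leaving this alone has several parts.

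- **The error would be noticed.** The appendix is headed as CTCAE v4.03 grading, and an output with every hemoglobin at Grade 3 would look absurd at once. That is probably true, but the repair would then be made outside the plan. A qualifier lost when the table was read from PDF cannot be wholly excluded either. However, the table has no column for conditions and the neighbouring rows are intact.
- **The first neutrophil row is not purely numeric.** Its Grade 3 and Grade 4 cells read "<1 Clinical Review Needed: Life-threatening consequences; urgent intervention indicated", so a condition may lie behind the row. If so, it is not stated, and the Grade 3 limit is applied to any count below 1.
- **The reach is narrow.** This stands. A reader might infer that the analyses for the primary safety objective are corrupted. The documents do not support that. Derived grades go only to listings, severity in the adverse event tables is recorded for each event (Listing 16.2.7.1), and Table 14.3.2 summarises the laboratory values themselves.

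Three further inferences are also not supported.

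- The 0 printed on a row marked as not done in the chemistry listing shell (16.2.8.1.1) is mock content. The governing note grades results, and Section 3.3 plans no imputation.
- The plan does not leave laboratory toxicity invisible by arm. Section 3.1 says of post-baseline extra draws "Otherwise, unscheduled data will not be used in the analyses, but will be presented in the listings", but Table 14.3.2 gives quartiles, minimum and maximum by arm at scheduled visits. A table of grade shifts would be an addition, not the correction of an error.
- A count of 8 visits × 24 subjects = 192 falsely flagged hemoglobins would be a ceiling. It borrows the visit days from the chemistry shell and assumes complete sampling.

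**Conclusion.** The point holds in a limited form. Two rows of Appendix 1 give wrong or conflicting grades as written, and no rule elsewhere in the SAP rescues them. The hemoglobin row is the consequential one: read literally, it puts essentially every result into Listing 16.2.8.2.2 and leaves none at Grade 0. The neutrophil row is minor, since it leaves open only whether a count below 0.5 is shown as Grade 3 or Grade 4. The effect is confined to the graded hematology listings, and no planned summary table changes.

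The conclusion rests on applying the rows literally to reported values. The only assumed inputs are the hemoglobin normal ranges, which affect the 14.2% illustration and the grades above the upper or just below the lower limit, but neither of the two defects.

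**What to change.** Make three edits to Appendix 1.

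1. Delete the first hemoglobin row, or state the reference it is measured against so that it is not applied to the raw value.
2. Delete the first neutrophil row, or state its condition so that a numeric count is graded by one row only.
3. Add a rule for a result that meets more than one row, for example the highest grade among the applicable rows. This rule cannot replace the first edit: with the hemoglobin row left as it is, taking the highest grade would fix every positive value at Grade 3 or above.

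The cost is two table rows and one sentence, plus the matching change in the grading program. No new data, table or listing is needed.
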